#### Oral Iron supplementation

As discussed in the Australian prescriber

- “Oral iron replacement is the most appropriate first-line treatment in the majority of patients. Its efficacy can be limited by poor patient compliance due to the high rate of gastrointestinal adverse effects and the prolonged treatment course needed to replenish body iron stores.”

From Australian medicines handbook (AMH) online the adverse effects of oral iron are:

- abdominal pain,
- nausea,
- vomiting,
- constipation,
- diarrhoea (all dose-related),
- Iron may cause your stools to turn black, but this is not harmful.
- Additional for oral liquid: temporary black discolouration of teeth

Very rarely, oral iron preparations can cause severe adverse reactions. Seek immediate medical attention if you notice any of the following symptoms:

- allergic reactions (rash; hives; difficulty breathing; tightness in the chest; swelling of the mouth, face, lips, or tongue);
- black, tarry stools;
- blood or streaks of blood in the stool;
- fever;
- Vomiting with continuing sharp stomach pain.

This is not a complete list of all possible side effects. Others may occur in some people and there may be some side effects not yet known.

---

### 2.3.2. KNOWN POTENTIAL BENEFITS

#### IV Ferric Carboxymaltose

As discussed in the NPS Medicinewise RADAR^24 “Ferric carboxymaltose (Ferinject) for iron-deficiency anaemia” (<https://www.nps.org.au/radar/articles/ferric-carboxymaltose-ferinject-for-iron-deficiency-anaemia>)

The efficacy of FCM for correcting IDA has been evaluated across a range of clinical conditions including inflammatory bowel disease, chronic kidney disease, chronic heart failure, menorrhagia and postpartum anaemia.

- Haemoglobin response similar to that with iron sucrose, but with fewer doses
  - Results from prospective and retrospective trials have confirmed that large doses of FCM given in fewer injections can increase Hb levels with efficacy comparable to that of multiple small dose injections of iron sucrose.
  - In the 8-week REPAIR-IDA trial, involving IDA patients with non-dialysis-dependent CKD, two doses of FCM (750 mg/dose, n = 1276) were shown to be non-inferior to a typical dosing strategy of iron sucrose (five or fewer infusions of 200 mg, n = 1285).
  - More people treated with FCM had a sustained Hb increase of  $\geq 10$  g/L from baseline to study end than for those given iron sucrose (48.6% vs 41.0%, 95% CI 3.6% to 11.6%).
- Mean increases in serum ferritin and transferrin saturation were also significantly greater in the FCM group compared with the iron sucrose group. The mean total iron dose received over the treatment phase was  $1464 \pm 158$  mg in the FCM group and  $963 \pm 138$  mg in the iron sucrose group.
  - Similarly, among patients with IDA and associated IBD, three or fewer 500-1000 mg FCM infusions showed improved efficacy compared with iron sucrose (up to 11 infusions of 200 mg iron) in the 12-week FERGIcor trial.
  - A small difference in mean total dose was reported for these treatment groups;  $1377 \pm 381$  mg (FCM) and  $1160 \pm 316$  mg (iron sucrose).
  - At the end of the study, 66% of the FCM cohort had experienced a  $\geq 20$  g/L Hb increase compared with 54% of the iron sucrose arm ( $p = 0.004$ ).

- More people in the FCM treatment group experienced correction of anaemia compared with the iron sucrose group at study end (73% vs 62%, respectively,  $p = 0.015$ ).
- The simpler FCM dosing regimen was also associated with greater patient compliance compared with iron sucrose ( $p < 0.001$ ).
- Improves anaemia as well as, or better than, oral iron and standard medical care
  - The efficacy of FCM for the treatment of iron-deficiency anaemia was compared with oral iron (ferrous sulphate) in several randomised open-label trials.
  - Overall, FCM ( $\leq 1000$  mg per infusion) was at least as effective, or more effective, than oral iron (ferrous sulphate 325 mg three times daily or 100 mg twice daily) at correcting haemoglobin, ferritin and transferrin saturation levels. Perhaps not surprisingly, haemoglobin increases were more rapid with FCM than with oral iron therapy.
- The comparative effectiveness of FCM in treating iron-deficiency anaemia versus standard medical care (including IV iron formulations) has also been investigated in several randomised controlled trials.
  - Clinically meaningful improvements in haemoglobin and iron indices have been observed compared with standard medical care in patients with IDA associated with conditions such as CKD, menorrhagia, IBD and after post-bariatric surgery or delivery.
- Clinical equivalence with IV iron polymaltose is not known
  - To date, there have been no head-to-head comparisons of FCM with iron polymaltose, which is FDM's main IV iron formulation comparator in Australia.
  - Indirect comparisons between FCM and iron polymaltose, based on their efficacy relative to oral iron, are also not possible due to marked heterogeneity in patients and outcomes.

### Oral Ferrous Fumarate

Oral iron therapy has been the mainstay of treatment for iron deficiency in children for many years. It is safe and **when taken over several months is** often effective at correcting iron deficiency with or without anaemia. Its efficacy is dependant on compliance and absorbance **both of which can be affected by common side effects** but it is generally well tolerated in the paediatric population. It has the added benefit of being cheap and easy to administer.

---

### 2.3.3. ASSESSMENT OF POTENTIAL RISKS AND BENEFITS

Preoperative optimisation of iron stores is an important part of minimising the risk of exposing our patients to a blood transfusion and reducing the burden of post operative anaemia. At the present time there is little preoperative screening in place for systemically well paediatric patients. Until recently patients were not undergoing routine screening bloods until the night before surgery preventing any preoperative treatment of iron deficiency or anaemia. In paediatric medicine oral iron is commonly used as first line therapy to replenish iron stores in those patients who are found to be iron deficient. Oral iron is cheap, relatively safe and easy to administer to children. However, oral iron therapy is often poorly tolerated due to side effects resulting in poor compliance and it is often ineffective even when taken regularly. This study aims to demonstrate that IV ferric carboxymaltose is superior to oral iron therapy in the correction of preoperative iron deficiency and prevention of severe post operative anaemia.

We feel the risks involved in this study are outweighed by the benefits to future patients that can be achieved through effective preoperative iron replacement. If IV ferric carboxymaltose is found to be superior to oral iron therapy then it maybe that the additional cost and risk of the IV formulation can be justified for the management of preoperative iron deficiency in

paediatric patients. If IV ferric carboxymaltose is not found to be superior to oral iron supplementation then this trial will support the continued use of oral iron and it may be possible to avoid the unnecessary cost and inconvenience of an intravenous iron infusion.

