There are two options for replacement of iron stores to correct iron deficiency. The traditional first line therapy is oral iron supplementation followed by intravenous iron therapy in those patients who fail to respond to oral iron. However, oral iron therapy takes time to work and is often poorly tolerated due to gastrointestinal side effects and for these reasons is commonly felt to not be a viable option in the preoperative patient who requires optimisation in a matter of weeks rather than months. Traditional intravenous iron preparations required up to 6 hours for safe infusion time which was a significant deterrent for many paediatric patients. However, with the new formulation of IV ferric carboxymaltose only requiring 15 minutes of infusion time and an improved risk profile, the balance of oral vs IV iron therapy is due to be revisited. Intravenous ferric carboxymaltose formulation has been demonstrated to be safe and effective in the treatment of iron deficiency due to inflammatory bowel disease in paediatric patients but its efficacy has not been trialed in the perioperative paediatric population.

This project aims to improve perioperative blood management through optimising preoperative haemoglobin and iron stores. There is significant data supporting the use of preoperative iron infusions in adult surgical patients, however this research has not been conducted in paediatric patients presenting for major surgery. This trial aims to assess the efficacy of preoperative intravenous (IV) ferric carboxymaltose iron infusion compared with traditional treatment of iron deficiency with oral iron therapy (ferrous sulphate liquid or ferrous fumarate tablets). If IV ferric carboxymaltose is found to be superior to oral iron therapy then it maybe that the additional cost and risk of the IV formulation can be justified for the management of preoperative iron deficiency in paediatric patients. If it is found that oral iron is as effective as IV iron then this information will help to change medical opinion of the role of oral iron in the preoperative setting.

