### 4. STUDY DESIGN

#### 4.1. OVERALL DESIGN

We will be conducting a single site, randomised control trial, open label, superiority design phase III trial. The null hypothesis states that there is no difference between oral and IV iron therapy in the incidence of severe anaemia at the time of discharge following elective spinal fusion surgery.

Bias will be minimised through computer generated block randomisation, allocation concealment in opaque envelopes, collecting objective data (haemoglobin and iron studies), blinding of outcome assessors and statistician.

There will be two study groups; those randomised to oral iron therapy (control group), and those randomised to IV ferric carboxymaltose (treatment group). There will be 17 patients

randomised to both the control and treatment arms. Patients will be consented and screened 6 weeks prior to their surgery and follow up will conclude at 12 weeks post operatively.

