## 9. STATISTICAL CONSIDERATIONS

### 9.1. STATISTICAL HYPOTHESES

- Primary Efficacy Endpoint(s):
  - Incidence of severe anaemia (Hb <100g/L) at time of discharge from hospital or 7 days postoperatively (whichever is sooner)
  - This trial is designed to demonstrate superiority of IV iron therapy over traditional oral iron therapy.
- Secondary Efficacy Endpoint(s):
  - Incidence of blood transfusion
  - Length of stay
  - Haemoglobin concentration and incidence of anaemia (Hb <120g/L) at 3 weeks postoperatively
  - Haemoglobin concentration and incidence of anaemia (Hb <120g/L) and incidence of iron deficiency (ferritin <30mcg/L) at 9 weeks postoperatively
  - Quality of functional recovery from surgery as measured by the SRS 30 at 9 weeks postoperatively

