### 9.2. SAMPLE SIZE DETERMINATION

The null hypothesis states that there is no difference between oral and IV iron therapy in the incidence of severe anaemia at the time of discharge following elective spinal fusion surgery. The primary outcome measure is the Incidence of severe anaemia (Hb <100g/L) at discharge from hospital.

Previous audit of 16 spine patients demonstrated a mean discharge Hb of 96g/L, with a standard deviation of 15.2. Haematocrit was not recorded.

Intravenous iron sucrose has been proven to increase Hb in adults with iron deficiency anaemia of various aetiologies that is non-responsive to oral iron by up to 50% (85.4g/L to 121 g/L) .

Whilst the figures for paediatric surgical patients' responsiveness to IV iron are not known (hence the development of the proposed study); it has been postulated that this may be likely to be similar to adults. Thus these preexisting findings in adults allow for an extrapolation of data to enable power calculation for the proposed study. Namely, that of the of patients being discharged with severe anaemia (Hb <10 g/dL) after spinal surgery - which currently number 68% of patients - should be able to be halved (50% decrease) through judicious and appropriate IV iron therapy.

In view of the lack of previously defined population characteristics, power calculations have been done using:

- a two study group design (Population rates of Discharge Hb<100 of 68.75% observed previously, compared to the expected post iron-infusion rates of Discharge Hb<100 of 34.38%, a figure chosen for reasons outlined above.)
- Further, while data will be collected in a continuous manner, it will be analysed as dichotomous, binomial data (two outcomes only: Hb >10 g/dL or Hb <10g/dL.) to reduce the number of patients required for the study.
- Assumption of alpha of 0.05, as per current medical research convention 
- Assumption of power (1-beta) of 0.8 as per current medical research convention 

This will result in an expected sample size of approximately 14 patients in the treatment group.

This figure has been reached using the following equation (fig. 1), which was selected to meet the above criteria . The calculation was performed using the on-line tool at <http://clincalc.com/stats/samplesize.aspx>.

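### Section 2.3.3 treats failure to show superiority as support for oral iron, although a superiority trial without a margin makes such a result inconclusive

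*Protocol*

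**What the plan says.** Protocol section 2.3.3, the assessment of risks and benefits, states what a null result would mean: if IV ferric carboxymaltose "is not found to be superior to oral iron supplementation then this trial will support the continued use of oral iron". The same sentence adds that the cost and inconvenience of an infusion, which it calls unnecessary, might then be avoided.

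The design sections describe a different kind of trial. Section 4.1 calls it a "superiority design phase III trial". Section 9.1 says: "This trial is designed to demonstrate superiority of IV iron therapy over traditional oral iron therapy". Section 9.2 says: "The null hypothesis states that there is no difference between oral and IV iron therapy in the incidence of severe anaemia". The protocol gives no equivalence or non-inferiority margin and no confidence-interval criterion for a conclusion in favour of oral iron.

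Section 2.2 contains a related sentence: "If it is found that oral iron is as effective as IV iron then this information will help to change medical opinion".

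**The concern.** Not rejecting a no-difference null does not show that the arms perform alike, whatever the sample size. To support oral iron from its own data, a trial must rule out a benefit of IV iron large enough to matter. That needs a margin, or at least an interval judged against one. Section 2.3.3 skips this step and gives a positive meaning to what may be missing evidence.

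The conclusion could influence practice. The protocol itself doubts oral iron in this setting: section 2.3.3 says that it often fails even with regular use, and section 2.2 says that it is commonly thought unsuitable when only weeks remain before surgery. If the planned effect were real but missed, section 2.3.3 would have the trial reported as favouring the arm with more severe anaemia.

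**Working it through.** **Inputs.** All come from section 9.2.
- Control rate: "Population rates of Discharge Hb<100 of 68.75% observed previously", so p0 = 0.6875. This equals 11/16, and the section reports: "Previous audit of 16 spine patients demonstrated a mean discharge Hb of 96g/L".
- IV rate: "expected post iron-infusion rates of Discharge Hb<100 of 34.38" per cent, so p1 = 0.3438.
- Planned difference: 0.6875 − 0.3438 = 0.3437, or 34.4 points.
- Alpha 0.05, two-sided (the formula uses 1.96). Intended power 0.80. Recruitment 17 per arm.

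**The protocol's own figure.** With p0q0 = 0.2148 and p1q1 = 0.2256:

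N = 0.2148 × {1.96 + 0.84 × √(0.2256/0.2148)}² / 0.3437² = 14.47

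The protocol states 14. Rounding up to 15 and allowing 10% attrition gives 15/0.9 = 16.7, or 17 per arm. The figure is reproduced. The formula compares one group with a fixed population rate, so it leaves out the sampling error of the randomised control arm. A two-arm calculation at the same rates needs 32 per arm.

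**How often a true halving would be missed.** The protocol names no primary test, so two common ones are assumed. Exact power is the sum, over all pairs (a, b) for which the test rejects, of Bin(a; n, 0.6875) × Bin(b; n, 0.3438).

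| Evaluable per arm | Test | Power | Missed |
|---|---|---|---|
| 17 | uncorrected chi-square | 55.8% | 44% |
| 17 | Fisher | 41.4% | 59% |
| 15 | uncorrected chi-square | 46.4% | 54% |
| 15 | Fisher | 30.9% | 69% |

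The rows for 15 per arm apply only if withdrawals are not replaced. Section 7.2 says that treated participants who withdraw will be replaced and that untreated ones may be, so 17 per arm is the main case.

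**What a null result would leave open.** With equal observed rates p and 17 per arm, the Wald 95% half-width is 1.96 × √(2p(1 − p)/17):
- p = 0.6875: 1.96 × √(0.4297/17) = 0.312, about 31 points.
- p = 0.50: 1.96 × √(0.5/17) = 0.336, about 34 points.

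These are half-widths; the full interval is about 62 to 67 points wide. Even identical arms would leave benefits of about 31 to 34 points barely excluded or not excluded. The Newcombe interval for 12/17 in each arm is slightly narrower, about ±29 points.

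**An example.** Suppose 12/17 oral and 7/17 IV patients have severe anaemia. The observed difference is 5/17 = 29 points in favour of IV iron, with Fisher p = 0.17. The uncorrected chi-square is not significant either. Superiority is not found, so section 2.3.3 says that the trial supports oral iron. The Newcombe 95% interval runs from −4 to +55 points and contains the whole planned benefit.

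**The case against.** The strongest reply is that oral iron is already the first-line treatment. Keeping it when a costlier alternative has not been shown better is the ordinary consequence of a superiority trial. The protocol speaks of continued use, does not claim equal efficacy in that sentence, and says only that infusions might be avoided. This stands as a reason for keeping the default. It does not rescue the statement that the trial itself will support oral iron, or the description of the infusion cost as unnecessary.

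Four stronger readings are tempting, and the documents do not support them.
- A reader might infer that section 2.2 makes the same error. It does not: it is conditional on a finding of equal effect and does not say that non-significance is such a finding. What it lacks is any criterion by which this design could make that finding.
- A reader might treat section 2.3.3 as a formal decision rule. It is part of the risk/benefit justification. Sections 9.1 and 9.4 attach no conclusion to a null result, and the analysis is left to a biostatistician.
- A reader might say that the trial would miss the planned effect at least half the time. At 17 per arm the range is 44% to 59%, which straddles half. The higher range of 54% to 69% assumes 15 per arm, contrary to the replacement rule in section 7.2.
- A reader might use the low power to make this a critical defect. The miss rate comes from the one-group sample-size formula. Rewording section 2.3.3 would not change it, and enlarging the trial would not turn non-significance into support.

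**Conclusion.** The point holds for section 2.3.3. A non-significant result in this superiority trial would be inconclusive, and the protocol should not say in advance that it would support oral iron. That follows from the design alone and depends on no power figure.

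The power figures show how often the wording could mislead: about 44% to 59% of trials if the true rates are 68.75% and 34.38%, with 17 evaluable per arm, two-sided alpha 0.05, and either an uncorrected chi-square or Fisher test. The choice of test is an assumption.

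The correction concerns a stated conclusion. It affects no endpoint, data collection or specified analysis, and it is not a fault that must be cured before the trial can run. The shortfall in power should be handled as a separate sample-size point.

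**What to change.** In section 2.3.3, replace the sentence on a non-superior result with: *If superiority is not shown, the risk difference and its 95% CI will be reported and the result described as inconclusive; no claim that oral iron is as effective will be made.*

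In section 2.2, add a note that this design has no criterion for finding oral iron as effective as IV iron.

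The change is to wording only, though the protocol requires ethics committee review of any amendment. The real cost is that the stated value of a null result becomes less favourable.

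If the sponsor wants to be able to conclude positively for oral iron, it would need a justified margin and a trial sized for it. As an illustration only, with both true rates at 68.75%, one-sided alpha 0.025 and 80% power, assumed margins of 20, 15 and 10 points need 85, 150 and 338 per arm. The protocol gives no margin.

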### 3. OBJECTIVES AND ENDPOINTS

OBJECTIVES	ENDPOINTS	JUSTIFICATION FOR ENDPOINTS
Primary		
To compare the efficacy of two forms of iron replacement therapy in the prevention of severe anaemia at discharge from hospital.	The primary endpoint is the incidence of severe anaemia (haemoglobin <100g/L) the time of discharge from hospital (or one week postoperatively, whichever one is sooner).	Severe post operative anaemia is a clinically relevant method to measure the impact of preoperative iron therapy. It is simple to measure and is not subjective to bias.
Secondary		
To compare the postoperative effect of preoperative correction of iron deficiency with two different forms of iron replacement.	
 
- Incidence of blood transfusion
 
- Length of stay
 
- 3-5 weeks postoperatively                             
 
- Haemoglobin concentration
 
- Incidence of anaemia (Hb<120g/L)
 
 
 
- 6-12 weeks postoperatively                             
 
- Haemoglobin concentration
 
- Incidence of anaemia (Hb <120g/L)
 
- Iron studies
 
- Quality of functional recovery from surgery as measured by the SRS 30.
 
 
 
	These endpoints are clinically relevant markers of recovery from surgery. Post operative recovery of haemoglobin concentration is a clinically important effect of adequate iron stores.

### 4. STUDY DESIGN

#### 4.1. OVERALL DESIGN

We will be conducting a single site, randomised control trial, open label, superiority design phase III trial. The null hypothesis states that there is no difference between oral and IV iron therapy in the incidence of severe anaemia at the time of discharge following elective spinal fusion surgery.

Bias will be minimised through computer generated block randomisation, allocation concealment in opaque envelopes, collecting objective data (haemoglobin and iron studies), blinding of outcome assessors and statistician.

There will be two study groups; those randomised to oral iron therapy (control group), and those randomised to IV ferric carboxymaltose (treatment group). There will be 17 patients

randomised to both the control and treatment arms. Patients will be consented and screened 6 weeks prior to their surgery and follow up will conclude at 12 weeks post operatively.

## 4.2. SCIENTIFIC RATIONALE FOR STUDY DESIGN

We have selected a randomised control trial comparing the efficacy of oral and IV preoperative iron therapy in order to determine if IV therapy is superior to oral therapy. At the present time oral iron is commonly used as first line therapy to replenish iron stores in those patients who are found to be iron deficient. Oral iron is cheap, relatively safe and easy to administer to children. However, oral iron therapy **requires time to be effective** and is often poorly tolerated due to side effects resulting in poor compliance. This study aims to demonstrate that IV ferric carboxymaltose is superior to oral iron therapy in the correction of preoperative iron deficiency and prevention of severe post operative anaemia.

If IV ferric carboxymaltose is found to be superior to oral iron therapy then it maybe that the additional cost and risk of the IV formulation can be justified for the management of preoperative iron deficiency in paediatric patients.

